MPNs	Myeloproliferative Neoplasms
MTD	Maximum Tolerated Dose
NOAEL	No Observed Adverse-Effect-Level
Ph-neg	Philadelphia Chromosome Negative
PHI	Protected Health Information
PV	Polycythemia Vera
PI	Principal Investigator
REDCap	Research Electronic Data Capture
RCM	Red Cell Mass
SAE	Serious Adverse Event
SOC	Standard of care
SUSAR	Suspected Unexpected Serious Adverse Reaction
UAP	Unanticipated Problem
VAF	Variant Allelic Frequency
WB	Whole Blood
WCM	Weill Cornell Medicine
WHO	World Health Organization

1. Protocol Summary

Full Title:	A two-tiered, phase II, rule-based, intra-patient dose escalation study to investigate safety and feasibility of vactosertib (TEW-7197 for the treatment of anemic patients with Philadelphia chromosome-negative Myeloproliferative Neoplasms (Ph-neg MPNs)
Short Title:	TGF β R1 inhibition in Ph-neg MPNs
Clinical Phase:	II
Principal Investigator:	[name]., Ph.D.
Study Description:	
This is a two-tiered single arm Phase 2 trial of vactosertib (TEW-7197) for the treatment of anemia in Ph-neg MPNs. Both tiers use a rule-based, accelerated dose escalation scheme to efficiently assess the potential of vactosertib to safely and effectively treat anemic patients with Ph-neg MPNs. The first tier of this trial (Tier 1) is an intra-patient dose finding study in 12 patients that uses a low starting dose of vactosertib for all patients. Treatment dose is escalated according to prospectively-defined rules, and a toxicity and treatment effect algorithm (Table 3 in section 7) during the period of 16 weeks (4 treatment cycles). If pre-established efficacy and safety endpoints are met (section 12.1), then Tier 1 of the study will be followed by a Tier 2 expansion study with an additional 25 patients for a period of 24 weeks (6 treatment cycles).
 
Vactosertib will be administered in combination with stable dose of current therapy. Prior to enrollment patients must be on a stable dose of their current therapy for 3 months prior to entering the study. For patients not receiving cytoreductive therapies (e.g., interferon, hydroxyurea, DNA hypomethylating agents or other cytotoxic chemotherapy) must be off their most recent for a period of at least 14 days or 5 half-lives, whichever is longer. Supportive care measures including packed red blood cell (PRBC) transfusions for HGB <7g/dL, or symptomatic anemia, will be permitted. Administration of erythropoiesis stimulating agents (ESAs), however, will not be permitted on the trial (patients recruited would have serum EPO >125 U/L above which the benefit of ESAs is not supported)¹.

Sample Size:	Total = 37 subjects (N = 12 for Tier 1, N = 25 for Tier 2)
Enrollment:	This study will enroll 37 subjects and screen up to 100 subjects.
Study Population:	Patients of age \geq 18 with anemia due to Ph-neg MPNs
Enrollment Period:	72 months

Study Design:

This is a two-tiered single arm Phase 2 trial of vactosertib (TEW-7197) for the treatment of anemia in Ph-neg MPNs. Both tiers use a rule-based, accelerated dose escalation scheme to efficiently assess the potential of vactosertib to safely and effectively treat anemic patients with Ph-neg MPNs. The first tier of this trial (Tier 1) is an intra-patient dose finding study in 12 patients that uses a low starting dose of vactosertib for all patients. Treatment dose is escalated according to prospectively-defined rules, and a toxicity and treatment effect algorithm (*Table 3 in section 7*) during the period of 16 weeks (4 treatment cycles). If pre-established efficacy and safety endpoints are met (*section 12.1*), then Tier 1 of the study will be followed by a Tier 2 expansion study with an additional 25 patients for a period of 24 weeks (6 treatment cycles).

Study Duration:

24 months (4 months for tier 1, 6 months for tier 2, and follow-up after intervention (2 months for patients who come off study and 12 months for patients completing study).

Participant Duration: Approximately 18 months

Study Agent: Vactosertib

Intervention Description:

Vactosertib is given oral twice a day for 5 days followed by 2 days off. The starting DL is 50mg BID (*see Table 2 in section 6 for DLs*). A cycle is defined as 4 weeks of treatment. **Primary Objective:**

- To establish a safe and tolerable dose and schedule of vactosertib in Ph-neg MPNs as determined by the study dose escalation algorithm (*Table 3 in section 7*).
- To preliminarily assess efficacy of vactosertib in treating anemic patients with Ph-neg MPNs as reported by symptomatic, splenic and/or erythropoietic response (*section 9.1*).
- To determine the safety and tolerability of vactosertib administered alone or in combination with cytoreductive therapies for MPN (approved and standard of care).

Secondary Objectives:

- To evaluate on target molecular activity of vactosertib in anemic patients with Ph-neg MPNs as determined by the following parameters:
 - Molecular response, measured by change in blood (and/or marrow) variant allelic frequency (VAF) of MPN driver mutations (JAK2, CALR or MPL).
 - Histologic response, measured by change in bone marrow biopsy cellularity and fibrosis grade.
 - SMAD2/3 phosphorylation measured by flow cytometry of peripheral blood and/or bone marrow hematopoietic cells and/or by immunohistochemical staining of bone marrow biopsy sections.
- To identify common toxicities of vactosertib in patients with Ph-neg MPNs.

Exploratory Objectives:

To assess the stem cell directed effect of vactosertib by quantifying the VAF of MPN driver mutations in stem, progenitor and mature cell populations isolated from PB or BM samples before and after treatment with vactosertib.

Endpoints:

Primary Endpoints: (Safety and Efficacy)

- Tier 1 (Safety endpoints):
 - Define the safest, minimally effective starting DL for Tier 2 ([section 5.3.5.1](#)).
 - Identify DLTs and, possibly the MTD of vactosertib in patients with MPN
- Tier 2 Efficacy endpoints ([section 9.1](#)):
 - Erythropoietic response as defined by the IWG-MRT criteria
 - Clinical response in symptoms as defined by IWG criteria.
 - Splenic response as defined by IWG criteria.^{2,3}
- Tier 2 Safety endpoints: Identify DLT and, possibly MTD

Secondary Endpoints:

- Histologic response defined by any reduction in grade of bone marrow fibrosis by histopathologic assessment at 16 weeks.
- Molecular response defined by a decrease in VAF of MPN-driver mutations (eg. JAK2, CALR, and MPL allelic ratio) in blood and/or bone marrow cells.
- Pharmacodynamic Response defined as any of the following:
 - Reduced immunohistochemical staining for SMAD2/3 phosphorylation in bone marrow biopsy sections (*See Figure 1*).
 - Reduced mean fluorescence intensity (MFI) of SMAD2/3 phosphorylation staining in peripheral blood and/or bone marrow HSPCs or mature progeny as assessed by flow cytometry (*See Figure 2*).
- The incidence of hematologic toxicities, infections, disease progression, thrombosis events, and the probability of overall and progression free survival, will be monitored.

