1.2 Study Objectives

1.2.1 Primary Objectives

- To establish a safe and tolerable dose and schedule of vactosertib in Philadelphia chromosome negative (Ph-neg) Myeloproliferative Neoplasms (MPNs).
- To preliminarily assess efficacy of vactosertib in treating anemic patients with Ph-neg MPNs as reported by symptomatic, splenic and/or erythropoietic response.
- To determine the safety and tolerability of vactosertib administered alone or in combination with available cytoreductive therapies for MPN (approved and standard of care).

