10.1. Response Criteria (Criteria for Clinical Benefit)

The following criteria are used to decide if subject can be offered the opportunity to receive more than 4 cycles of vactosertib AND for decision to proceed to the Tier 2 expansion phase after Tier 1. These are adapted from the IWG-MRT and ELN consensus reports on response determination in patients with MPNs.

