10.1.1 Symptomatic Response

- Defined by a reduction in MPN-SAS total score by $\geq 50\%$ compared to pretreatment score.

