10.1.2 Splenic Response

Defined by:

- Non-palpable spleen when baseline spleen size was 5-10 cm below left costal margin;
- At least 50% reduction in spleen size when baseline spleen is > 10 cm below left costal margin
- At least 35% reduction in spleen size as assessed by US, CT or MRI.

Note: A baseline spleen size < 5 cm below left costal margin is not eligible for spleen response;

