12.4.2 Analysis of Secondary Endpoints

Clinical response to vactosertib will be assessed using the *Criteria for Clinical Benefit* outlined above as a composite endpoint. Patients achieving any of these criterial will be considered to have achieved clinical benefit. This endpoint will be used to define a preliminary estimate of the potential efficacy of vactosertib in the study population. Complete enrollment to both tiers (37 total) will allow us to confidently identify a *Clinical Benefit* response rate of more than 30%. This estimate has a significance of ≤ 0.1 and a power of 0.8 and is based upon a reported clinical improvement rate of $\leq 10\%$ (almost

entirely due to symptomatic response) in similar patient populations with best available therapy^{34,35}. Reported rates of splenic and/or erythropoietic responses to best available therapy are $\leq 3\%$. The 37 subjects enrolled on this study will allow Splenic Response and Erythropoietic Response rates of at least 20% to be individually tested with a power of 80% and a significance of $< 0.1\%$. If after complete accrual of 37 subjects, more than 11 patients meet criteria for Composite Response, or more than 7 patients meet criteria for Splenic or Erythropoietic Response, vactosertib will be considered to have sufficient efficacy for definitive testing in a randomized study.

The secondary endpoints of erythropoietic (HGB and RBC transfusion), symptomatic, and splenic responses will be directly tested as described in the preceding section. While limited by the small sample size, additional endpoints will be assessed including molecular (MPN driver variant allele frequency), pharmacodynamic (SMAD2/3 phosphorylation in bone marrow and/or blood CD34+ hematopoietic stem and progenitor cells), and histologic (bone marrow cellularity and fibrosis score) responses. The incidence of hematologic toxicities, infections, disease progression, thrombosis events, and the probability of overall and progression free survival, will be monitored. Secondary endpoints will be reported using descriptive statistics but no formal hypothesis testing will be performed.

Other secondary endpoints will be reported using descriptive statistics but no formal hypothesis testing will be performed. The following endpoints will be analyzed:

12.4.2.1 Histologic response defined by any reduction in grade of bone marrow fibrosis by histopathologic assessment at 16 weeks.

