The principal investigator will be primarily responsible for monitoring the safety of the study, adverse events, both serious and non-serious and deaths that occur during study participation by subjects. All adverse events will be monitored until they resolve or are clearly determined to be due to a subject's disease or intercurrent illness(es).

At the completion of Tier 1, all data necessary to evaluate [Criteria for Decision to Proceed to Tier 2](#) section) will be reported to WCM Statistician, WCM DSMB and Medpacto. The Simon Two-stage

Optimum Design is expected to minimize the number of subjects exposed to vactosertib if it is found to be an unsuitable agent for the treatment of anemic patients with Ph-neg MPNs. If 1 or more subjects meets the endpoint then the study will proceed to Tier 2 and another 25 subjects will be enrolled). This decision will be submitted to WCM IRB at the time of continuing review.

After completion of Tier 2, all data necessary to evaluate will be reported to WCM Statistician, WCM DSMB and Medpacto. If four or more subjects meet the Composite Response & Toxicity Endpoint then vactosertib will have shown preliminary efficacy and feasibility to justify further evaluation as an agent to treat anemic patients with Ph-Neg MPNs. This interpretation will be submitted to WCM IRB at the time of continuing review.

Should the Stopping Rules for [Tier 1](#) or for [Tier 2](#) be met, accrual of new subjects will be immediately suspended and the WCM IRB and Medpacto will be notified. The study DSMB will meet to review study data. The DSMB may either recommend permanent closure of the study or may allow protocol revision/amendment and submission to WCM IRB for review. DSMB recommendations will be submitted to Medpacto and WCM IRB.

All protocol amendments and consent form modifications will be made by the Principal Investigator. Medpacto will have the opportunity to review and approve the changes prior to submission of these changes to the local IRB.

[Section 7.9, Criteria for Removal from Study](#), details treatment stopping rules for individual patients.

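### A go under the 4-of-37 rule does not by itself support a conclusion about anemia, because neither efficacy rule requires an erythropoietic responder

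*Combined protocol and SAP*

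**What the plan says.** **Purpose.** The Protocol Summary states: "This is a two-tiered single arm Phase 2 trial of vactosertib (TEW-7197) for the treatment of anemia in Ph-neg MPNs". Section 4.2 makes anemia an entry criterion. In Table 3 (section 7.7.2) the efficacy inputs to dose adjustment are hemoglobin and red-cell transfusion.

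**Objective and endpoints.** Section 1.2.1 is broader: "To preliminarily assess efficacy of vactosertib in treating anemic patients with Ph-neg MPNs as reported by symptomatic, splenic and/or erythropoietic response". The Protocol Summary lists erythropoietic, symptom and splenic response as Tier 2 efficacy endpoints and does not rank them.

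**What counts as a response.** Section 10.1 gives three Criteria for Clinical Benefit, also used "for decision to proceed to the Tier 2 expansion phase after Tier 1":
- Symptomatic (10.1.1): "Defined by a reduction in MPN-SAS total score by" at least 50%.
- Splenic (10.1.2): for example "Non-palpable spleen when baseline spleen size was 5-10 cm below left costal margin".
- Erythropoietic (10.1.3): a hemoglobin rise of 1.5 g/dL, or a reduced transfusion need.

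Section 10.1 does not say how the three combine. Section 12.4.2 does: "Patients achieving any of these criterial will be considered to have achieved clinical benefit". Table 5 adds that benefit must last at least 8 weeks and that no dose-limiting toxicity occurs.

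**Go rule.** Table 4 requires at least 1 responder among 12 to open Tier 2 and at least 4 among 37 at the end. Section 15 repeats this: "If four or more subjects meet the Composite Response & Toxicity Endpoint then vactosertib will have shown preliminary efficacy and feasibility". Section 12.4.1 refers the primary analysis to Table 4 and section 12.1 only.

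**Second rule and background rates.** Section 12.4.2 also calls efficacy sufficient for a randomized study if more than 11 of 37 meet the composite, or more than 7 meet the splenic or erythropoietic criteria. It puts clinical improvement on best available therapy at no more than 10%, almost "entirely due to symptomatic response) in similar patient populations with best available therapy", and splenic and/or erythropoietic response at no more than 3%.

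**The concern.** Entry and dose adjustment both turn on anemia, but the decision at the end does not. Four durable symptom responders with stable hemoglobin and unchanged transfusion need would satisfy section 12.1.1. By the plan's own background figures, the symptom score is the component most easily met. It is also patient-reported in an open-label, single-arm trial.

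What is at stake is how a positive result is read. Sections 12.1.1 and 15 take four composite responders as grounds to evaluate the drug further for anemic patients. A reader who holds that next to the Study Description would take a go as evidence of an effect on anemia. Erythropoietic response is listed among the Tier 2 efficacy endpoints, yet the primary analysis gives it no threshold of its own.

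**Working it through.** **Inputs.** Stages of 12 and 25 patients, cut-offs of at least 1 and at least 4, null 5% and target 20% (Table 4). Background rates of at most 10% and at most 3% (section 12.4.2). Section 12.2.2 cites section 9.1 for the benefit criteria; I take section 10.1 as meant, since the criteria stand there.

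**Step 1: reproduce the design.** With per-patient composite rate p,

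P(go) = Σ (x = 1 to 12) P(X₁ = x; 12, p) × P(X₂ ≥ 4 − x; 25, p).

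- p = 0.05: 0.0935
- p = 0.20: 0.9024, so the type II error is 0.0976
- Early stop at p = 0.05: 0.95¹² = 0.540

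Both error rates are below 10% as stated. The two-stage arithmetic is correct.

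**Step 2: split responders by component.** Let e be the rate of patients who respond through 10.1.3 (with or without another response), q the rate who respond only through symptoms or spleen, and s = 1 − e − q. Then

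P(go, no erythropoietic responder) = Σ over x₁ ≥ 1, x₁ + x₂ ≥ 4 of C(12, x₁) q^x₁ s^(12−x₁) × C(25, x₂) q^x₂ s^(25−x₂).

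The at-most-one figures use the same enumeration with three categories. The splits are assumptions within the ceilings of section 12.4.2.

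| e + q | P(go) | P(go, none erythropoietic) | Share of go with none | Share of go with at most one |
|---|---|---|---|---|
| 3% + 2% (plan null) | 9.3% | 0.18% | 2% | 14% |
| 3% + 7% | 44.7% | 7.6% | 17% | 52% |
| 1% + 9% | 44.7% | 26.0% | 58% | 91% |

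With e = 0, every go lacks an erythropoietic responder, and P(go) is 9.3%, 21.9% and 44.7% at q = 5%, 7% and 10%.

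**Step 3: does the second rule close the gap?** Twelve symptom responders meet its first limb and eight splenic responders its second, so it does not require an erythropoietic responder. As an erythropoietic cut-off it is also weak: P(X ≥ 8; 37, 0.20) = 46.7%, against the 80% power that section 12.4.2 states for a 20% rate.

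**Step 4: properties of an added erythropoietic condition.** This is P(at least 1 composite responder in the first 12 and at least 4 erythropoietic responders in 37):

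| Erythropoietic rate | Other-only rate | Probability |
|---|---|---|
| 3% | 2% / 7% / 17% | 2.1% / 2.3% / 2.4% |
| 5% | 5% / 15% | 10.2% / 11.0% |
| 20% | 0% / 7% | 90.2% / 93.8% |

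Whatever the other-only rate, it cannot exceed the single-stage value P(X ≥ 4; 37, e), which is 2.4% at 3% and 11.2% at 5%.

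**The case against.** The strongest reply is that nothing is hidden. The primary objective names symptomatic, splenic and/or erythropoietic response, the title speaks of anemic patients, and the go statement claims only preliminary efficacy and feasibility for further evaluation. A reader might infer that the plan declares the drug effective against anemia. The documents do not say that, and the mismatch is with the Study Description. This part of the reply stands.

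A reader might also infer that go decisions with no erythropoietic responder would be common under the plan's own null. They would not: 0.18% of trials at 3% + 2%. Nor is a 90% go probability at a 20% composite rate a false go, because 20% is the level Table 4 calls substantial activity. The 44.7% at a 10% composite rate partly reflects a separate matter, a 5% null set below a background of up to 10%.

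Finally, section 12.4.2 does plan to test splenic and erythropoietic response individually. But its rule joins its limbs by an or, sits under secondary endpoints for which the same section disclaims formal testing, and does not modify the 4-of-37 rule.

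Rewording the Study Description would remove the mismatch. It would still leave erythropoietic response, a listed Tier 2 efficacy endpoint, with no threshold in the primary analysis.

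**Conclusion.** The point holds in a limited form. The composite is prespecified and its two-stage arithmetic is sound, but a go does not by itself support a conclusion about anemia, because neither efficacy rule requires an erythropoietic responder. That follows from the text at any response rate.

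The size depends on assumed rates. The 10% and 3% are upper limits, carry no 8-week or toxicity condition, and the 3% covers splenic and erythropoietic response together. So 44.7% is the upper end for P(go) at background rates. The 17% share with no erythropoietic responder is not an upper limit: it rises to 58% if only 1% of patients respond erythropoietically. The calculation treats patients as independent with common rates. The change is worth making because it alters what a positive result may claim.

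**What to change.** Keep the 4-of-37 composite as the two-stage go rule. Add to sections 12.1.1 and 15:

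*Activity against anemia is concluded only if at least 4 of 37 patients meet Table 5 through the erythropoietic criterion (section 10.1.3). If the composite is met otherwise, the conclusion is limited to symptom or splenic benefit. Responders are reported by component.*

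Reconcile section 12.4.2 so that only one erythropoietic cut-off remains, since the existing more-than-7 figure does not deliver its stated power. State the properties of the new condition: a false anemia claim in 2.1–2.4% of trials at a 3% erythropoietic rate and 10.2–11.0% at 5% (with 5–15% other-only responders), and power of 90–94% at 20%. The 5% figures lie slightly above the plan's 10% type I error and should be disclosed.

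The cost is a few sentences, one table and the edit to section 12.4.2. The sample size stays at 37 and the component data are already collected. The downside is that a symptom-only or spleen-only signal would no longer support an anemia claim.

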1.1 Schema

Section 6.1, Schedule of Assessments, e.g., Visit 1; Visit 2; etc.

Prior to Enrollment

Obtain informed consent. Screen potential participants by inclusion and exclusion criteria; obtain history, document.

Tier 1
12 participants

Tier 2
25 participants

D0 (C1D1)

Perform baseline assessments, provide drug.
Section 6.1, Schedule of Assessments

Visit 2-16 (tier1)
Visit 2-24 (tier2)

Follow-up assessments, safety and efficacy evaluation and dose titration, refer to
Section 6.1, Schedule of Assessments for assessments and follow up intervals

Visit X (end of tier 1, end of tier2)

Final Assessment of study endpoints and safety
Section 6.1, Schedule of Assessments

1.2 Study Objectives

1.2.1 Primary Objectives

- To establish a safe and tolerable dose and schedule of vactosertib in Philadelphia chromosome negative (Ph-neg) Myeloproliferative Neoplasms (MPNs).
- To preliminarily assess efficacy of vactosertib in treating anemic patients with Ph-neg MPNs as reported by symptomatic, splenic and/or erythropoietic response.
- To determine the safety and tolerability of vactosertib administered alone or in combination with available cytoreductive therapies for MPN (approved and standard of care).

1.2.2 Secondary Objectives

- To evaluate the on target molecular activity of vactosertib in anemic patients with Ph-neg MPNs. This will be determined by the following parameters:
 - Molecular response, measured by change in blood (and/or marrow) allelic ratio of MPN driver mutations (JAK2, CALR or MPL).
 - Histologic response, measured by change in bone marrow biopsy cellularity and fibrosis grade.
 - SMAD2/3 phosphorylation measured by flow cytometry of peripheral blood and/or bone marrow hematopoietic cells or by immunohistochemical staining of bone marrow biopsy sections.
- To identify common toxicities of vactosertib in patients with Ph-neg MPNs.

1.2.3 Exploratory Objectives

To assess the stem cell directed effect of vactosertib by quantifying the VAF of MPN driver mutations in stem, progenitor and mature cell populations isolated from PB or BM samples before and after treatment with vactosertib.

2. Background

